With the above comments in mind and with the focus of the study being on a between-group comparison of the change from baseline to 24 months, the primary analysis will be an analysis of covariance with the 24-month value as the dependent variable and with the baseline value as a predictor variable. The statistical model we employ reflects the parametrization described by Baldwin and Colleagues.⁶⁰ It takes the initial form $Y_{24ij} = \beta_{0j} + \beta_{1j}X_{ij} + Y_{0ij} + e_{ij}$. In this model, Y_{24ij} is the 24-month value of the percent over the age and sex matched 50th BMI percentile (the primary outcome) for subject i and cluster j , with the “clusters” being defined by the coach in the intervention group and by individual children in the control group; β_{0j} and $\beta_{1j}X_{ij}$ are the intercept and intervention effect for cluster j ; Y_{0ij} is the baseline value of the outcome measure; and e_{ij} is the normally distributed error term. *In these models, the intercept and baseline are fixed effects while the intervention effect is random (DSMB approved protocol addenda, 11.2.18).* To reflect the partial clustering structure of the IRGT design, the above expression is modified by using the cluster-level equations $\beta_{0j} = \lambda_{00}$ and $\beta_{1j} = \lambda_{10} + \mu_{1j}$ to describe how the coefficients β_{0j} and β_{1j} vary across clusters. *The reparametrization of β_{1j} yields two random effects (DSMB approved protocol addenda, 11.2.18)* and the term μ_{1j} permits between-cluster variability in the outcome measure only within the intervention group (coded as 1). Substituting in the initial equation above yields the final model:

$$Y_{24ij} = \lambda_{00} + \lambda_{10}X_{ij} + \mu_{1j} X_{ij} + Y_{0ij} + e_{ij}$$

Using PROC MIXED in SAS, separate covariance structures will be fit to the FBT group and the UC group to account for the fact that the coach is nested within the site in the FBT group while there is no such nesting in the UC group. All analyses other than the above are secondary or exploratory analyses. One of those secondary analyses will supplement the primary analysis by adjusting for the sex and race of the participating child, family income, the educational level of the participating parent, and whether there are one or two parents in the household. These secondary analyses will provide insight regarding the impact the covariates may have on the primary outcome.

1. Sample Size and Statistical Power

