In translating the above decrease of 10.6 ± 15.3 in percent over BMI at 24 months into the setting of the proposed research, we emphasize that the seven referenced studies implemented FBT in controlled academic settings where we anticipate better performance than is likely in the family practices we will employ in this study. To estimate the degree to which the effect is likely to be attenuated when we switch from highly controlled to more “real life” settings, we considered the following. The child weight management intervention MEND (Mind, Exercise, Nutrition, Do it) focused on children age 7-13 who exceeded the 91st weight percentile. MEND employed both (1) a community-based mass-implementation intervention⁶⁸ involving many programs and 9563 subjects who provided complete data and (2) a rigorous randomized trial⁶⁹ (N=116) analogous to the seven [name] studies referenced in the preceding paragraph. The 12-month results were reductions in BMI of 0.79 kg/m^2 in the community study as compared to 1.04 kg/m^2 in the intervention arm of the randomized trial. Thus, the reduction in the community-based MEND intervention was 76.0% of the magnitude that was observed in the family-based arm of the randomized trial.

Based on this 76.0%, our computations conservatively assume changes in the intervention group that are 50%, 60%, and 70% of the previously observed change of 10.6 ± 15.3 that was observed in the rigorous academic environment of [name] studies.^{20,62-67} Thus, we base our power on a comparison of projected reductions of 5.3 ± 15.3 (50% of 10.6 ± 15.3), 6.4 ± 15.3 (60% of 10.6), and 7.4 ± 15.3 (70% of 10.6) in the FBT group as compared to 0 ± 10.08 in the UC group. In addition, given projected standard deviations of 15.3 and 10.08 in the two groups, we use the maximum and the mean of those two values and thereby compute power assuming standard deviations of both 15.3 and 12.7. In performing the calculations summarized below, we emphasize that we will have actual or imputed 24-month data on all subjects. To see details of how we will impute the 24 month values when necessary, please see the section below titled “Implementation of the Intention-to-Treat Principle.”

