--	--	----------	------------	--------------	--------------	--------------	--------------	--------------	--------------	--------------	--------------

2. Rationale for Percent Over BMI as the Primary Dependent Variable for Child Weight Change

We will use the percent over the 50th percentile BMI for our primary dependent measure for the children.⁶¹ This is commonly labeled as percent over BMI. This measure compares the child BMI to children who are at the average BMI for same age and sex. Twenty percent over the average value is approximately equivalent to the 85th BMI percentile. Using this metric, based on our previous research,²⁰ we expect a reduction in percent over BMI at 2 years of at least 5.3 due to the impact of the intervention. One of the strengths of this measure is the large database of studies that have used this measure.

There are other approaches to assessing child relative weight change, which include percent over the 95th BMI percentile and zBMI. Percent over the 85th or 95th BMI percentile is a recently developed measure that has an advantage of comparing children to children with overweight or obesity, rather than to the average weight child. In other words, when using the percent over the 85th BMI percentile, a positive number means the child is overweight, and a negative number means they are below the 85th BMI percentile. We have assessed the relationship between values obtained using the percent over 50 versus percent over 85 or percent over 95 in a sample of 987 children, and to no surprise, they are correlated greater than 0.98. However, this does not mean they are equivalent. Using our database of children for whom we have 10-year follow-up,^{62,63} we have also calculated the effect sizes for a sample of 193 children who we have studied for 10 years, which provides the largest and only dataset of truly long-term changes in the behavioral childhood obesity literature. The effect sizes for the different measures are similar at the end of treatment, being about 0.80, but they diverge as the length of the follow-up increases. As shown in Figure 1 below, the effect size gets smaller as length of follow-up increases, up to approximately the five-year follow-up, when the effect size increases for the percent over 85 and percent over 95, but not for the percent over 50. Thus, the percent over 50 that we have been using is the most conservative approach to assessing change in child relative weight among the percent overweight measures.

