Our handling of missing data begins with consideration of the pattern of missingness. If missing data in longitudinal analyses are missing completely at random or at random, they do not produce bias. In this setting, we will apply our random coefficient models to all data that are available. However, because this approach can yield a meaningful decrease in statistical power if

large amounts of data are missing, we will use multiple imputation⁷¹⁻⁷³(using PROC MI in SAS) to impute missing values when missingness is excessive and will treat this imputation approach as a sensitivity analysis. When data are not missing at random, ignoring the pattern of missingness can yield biased analyses.

We will begin our consideration of missing data while the trial is being implemented so we can minimize the amount and best understand the pattern of missingness. First, we will do everything we can to determine why subjects drop out of the study early and we will ask non-dropouts the reason for missing a particular visit. If data are missing, for example, because of bad weather, it may be likely that they are randomly missing whereas a family that drops out because the child is not losing weight will suggest non-ignorable missingness. Information such as this will help guide our analytic strategy. Second, we will encourage subjects who wish to drop out early to continue to provide key follow-up data, at 24 months in particular. Our experience is that many dropouts appreciate the scientific value of their contributions and are willing to cooperate in this way. Third and most importantly, we will do all we can do avoid dropout and missing data in the first place. In the recently completed 24-month multicenter COMPASS study, we collected 24-month data on 165 of 172 children in randomized families (95.9%) and 18-month data on five of the 7 who were missing at 24 months. Because the COMPASS intervention was performed at our own facilities with us having complete control, the dropout rate is likely to be higher in the proposed research where we rely on family practices. Nevertheless, if we can come close to the low missing data rate in COMPASS, the potential problem posed by missingness will be very limited.

The section that follows on the implementation of the intention-to-treat principle provides further insight into the handling of missing data (DSMB approved protocol addenda, 11.2.18).

7. Implementation of the Intention-to-Treat Principle

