The primary analysis will be an intention-to-treat analysis of the child that includes all subjects. Recalling that the primary analysis involves an analysis of covariance with the 24-month value of percent over BMI (the primary outcome measure) as the dependent variable, the inclusion of all subjects will reflect the following three considerations.

1. If the 24-month value of the primary outcome is available, the child will be included in the primary analysis without the need for further considerations.
2. If the 24-month value of height and/or weight (the defining components of the primary outcome) is missing and the child had height and weight data collected by his or her pediatrician at a clinic visit that occurred within 30 days of the targeted 24-month PLAN assessment, the following considerations will be used in imputing the 24-month value to be used in the primary analysis. Those considerations are designed to account for the anticipated imprecision of values measured at the pediatrician's office.
 - a. Within each clinic, a regression model that will allow us to impute 24-month values will be generated. Using all PLAN children who attend a particular clinic and who have both precisely measured PLAN height and weight data and less precise height and weight data measured at the clinic within 30 days of the PLAN measurement, clinic-specific regression models will separately predict the true height and weight using the age and sex of the subject as well as the height and weight value measured at the clinic. The goal will be to perform these calculations on a clinic-specific basis because the causes and magnitude of measurement error may differ

from clinic to clinic. However, if the number of subjects at a clinic who have the requisite height and weight data is less than 15 (less than 5 times the number of predictors), we will use all data from all clinics at the relevant study site to perform the desired imputation.

- b. Recalling that the children of interest in this scenario have clinic data collected within 30 days of the targeted 24-month PLAN assessment, the clinic-specific height and weight value calculated above will be used to impute the PLAN 24 month values from the contemporaneous value measured at the clinic. This imputed value will be used in the primary analysis.

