- c. If there is no clinic visit within 30 days of the 24-month target but there are visits both before and after the 24-month time point, we will interpolate linearly between predicted height and weight values at those time points to determine the predicted 24-month value. *Because we will only employ this option if height and weight data are available no more than three months before and three months after the target date for the 24-month visit, we anticipate that this interpolation approach will be performed infrequently in practice (DSMB approved protocol addenda, 11.2.18).*

3. If the 24-month value of height and/or weight is missing and the child did not have height and weight data collected by his or her pediatrician at a clinic visit that took place within 30 days of the planned 24-month assessment and did not have height and weight data measured at the clinic *within three months* both before and after the targeted 24-month visit, the 24-month value will be imputed using multiple imputation (*DSMB approved protocol addenda, 11.2.18*). Variables that will be used to facilitate the imputation process will be baseline height and weight, age, sex, and race. Any height and weight data collected using PLAN assessments at 6, 12, or 18 months will also be included in the multiple imputation.

Two points about the methods discussed in this section are in order. First, the rational for using multiple imputation only after it has been determined that clinic visit data are not available as a vehicle for imputing values is as follows. We anticipate that while values measured at the clinic will not employ the same rigor that will be employed in our protocol governed visits every six months, it is likely that the magnitude of the error will be relatively small and probably systematic rather than random within clinics. We therefore anticipate that this use of real measured data will yield more accurate results than multiple imputation. This is especially so for individuals who provide no data beyond their baseline measurement.

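### The multiple-imputation variables for the primary outcome omit randomised arm, which shrinks a true FBT–UC effect by an amount set mainly by how many children have baseline data only

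*Combined protocol and SAP*

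**What the plan says.** The primary analysis covers every randomised child: "The primary analysis will be an intention-to-treat analysis of the child that includes all subjects" (B.7, Implementation of the Intention-to-Treat Principle). The model is stated under B, Primary Analysis: "the primary analysis will be an analysis of covariance with the 24-month value as the dependent variable", with baseline value and arm as predictors.

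Missing 24-month values are handled in order. Item 2 of B.7 uses a pediatrician's height and weight taken within 30 days of the target date, or interpolates between clinic visits lying within three months on each side. Item 3 sends everyone else to multiple imputation. On the variables it says "Variables that will be used to facilitate the imputation process will be baseline height and weight, age, sex, and race", then "Any height and weight data collected using PLAN assessments at 6, 12, or 18 months will also be included in the multiple imputation". Arm appears in neither sentence, and no other section says that imputation is by arm.

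The rationale that follows prefers clinic data over multiple imputation and adds: "This is especially so for individuals who provide no data beyond their baseline measurement". The sample size section relies on the result: "we emphasize that we will have actual or imputed 24-month data on all subjects". Secondary Aim 1 applies the same strategy to parent BMI.

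**The concern.** An imputation model should carry at least the structure of the analysis it feeds. Here the analysis exists to estimate an arm difference, and the listed imputation variables contain no arm. For a child with interim visits, arm can enter indirectly through the 6-, 12- or 18-month measurements. For a child with baseline data only, it cannot enter at all. Drawn from such a model, FBT and UC children of this kind have the same expected 24-month value, so they dilute the contrast.

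The primary estimate itself is affected. The plan also makes a baseline-only group plausible: it expects more dropout than in the earlier trial (Missing Data) and expects it mostly in the first six months (Assessment Participation benchmarks). The size of that group is not given.

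**Working it through.** **Inputs from the documents.** Effect 5.3 and SD 15.3 (Sample Size and Statistical Power); 1:1 allocation (Recruitment); earlier trial, 24-month data on 165 of 172 children and 18-month data on five of the other seven (Missing Data); 20% planning dropout (Study Halting Rules); early change followed by levelling off (Longitudinal Analyses of Child Outcome Data).

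**Assumed inputs.** Missing at random given arm; effect at 6/12/18/24 months equal to 0.7/0.9/1/1 of its final size; three correlation structures for change (random walk, autoregressive 0.9, compound symmetry 0.8); the dropout splits and clinic recovery in step 4.

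**1. The plan's own figure.** 165/172 = 95.9%, as stated. Missing: 7/172 = 4.1%. Baseline-only: at most 2/172 = 1.2%, because five of the seven were seen at 18 months.

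**2. Baseline-only children.** Without arm, both groups are drawn around the pooled mean. With equal arms, UC children with no follow-up are credited with 5.3/2 = 2.65 points and FBT children lose the same. The expected estimate is 5.3 × (1 − p), where p is the baseline-only share.

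| p | Formula | Simulated, no arm |
|---|---|---|
| 2% | 5.194 | 5.197 |
| 5% | 5.035 | 5.037 |
| 10% | 4.770 | 4.771 |
| 20% | 4.240 | 4.235 |

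With arm in the model, the simulated estimate returns to 5.27–5.30. The simulation assumes a baseline SD of 25. The formula needs no correlation assumption.

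**3. Children with interim visits.** The share of the contrast retained, r, is the pooled regression of 24-month change on the observed changes, applied to the arm effects at those visits. Example (random walk, last seen at month 6): variance of change = 15.3²/4 = 58.5; slope = (58.5 + 2.65² × 0.7)/(58.5 + 2.65² × 0.7²) = 63.4/62.0 = 1.02; r = 1.02 × 0.7 = 0.72. Across the three structures:

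- last seen at 6 months: 0.52–0.72
- last seen at 12 months: 0.72–0.91
- last seen at 18 months: 0.81–1.00

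**4. Total loss** = p(baseline-only) + Σ p(last seen at k) × (1 − r at k).

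- *Earlier trial's missingness, the two remaining children taken as baseline-only:* 2/172 + (5/172) × (0 to 0.19) = 1.2% to 1.7%. The effect of 5.3 becomes 5.24 to 5.21.
- *20% missing, all seen at 18 months:* 0.20 × (0 to 0.19) = 0 to 4%.
- *Illustration: 20% missing, half baseline-only, the rest last seen evenly at 6, 12 and 18 months, no item-2 recovery.* Low end: 0.10 + 0.0333 × (0.28 + 0.09 + 0) = 11%. High end: 0.10 + 0.0333 × (0.48 + 0.28 + 0.19) = 13%. A large simulation (random walk) gave 4.67 without arm and 5.27 by arm, against a true 5.31.
- *Same, with item 2 supplying half of the missing values evenly:* half of 11–13%, about 6%.

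**5. True effect zero.** There is no contrast to dilute. In a simulation with no effect the mean estimate was −0.04 and the rejection rate 0.018, so the error does not favour FBT.

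**6. Non-ignorable dropout.** In the illustration, suppose the baseline-only FBT children gain nothing. The true intention-to-treat effect is 0.9 × 5.3 = 4.77. By-arm imputation returns 5.3, and 5.3/4.77 = 1.11, so it is 11% too large. The simulation gave 4.72 without arm, 5.32 by arm and 4.79 with control-based imputation.

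**7. Sensitivity analyses (section E).** Analysis 1 drops children with no follow-up but keeps item-3 imputation for the rest. In the illustration it still loses 0.0333 × (0.37 to 0.95)/0.90 = 1.4% to 3.5%. Analysis 2 (no imputation) and analysis 4 (random coefficient models) do not use this imputation.

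**The case against.** - **The list may not be exhaustive.** It names variables that assist imputation, so arm could still be added in the code. That is possible, but a pre-specified primary analysis should not rest on an unstated variable.
- **Multiple imputation is only a sensitivity analysis.** The Missing Data section says this about the secondary random coefficient models. B.7 item 3 puts it in the primary analysis.
- **The plan works hard to avoid the problem.** It provides home visits, remote assessments, medical-record data after discontinuation, and requests for 24-month data from dropouts. This stands: recovery could be substantial. Its yield is not stated, and the item-2 windows are narrow.
- **The loss is small and conservative.** At the only documented missingness it is 1–2%. Analyses 2 and 4 would expose a larger one, though neither corrects the primary estimate.
- **Leaving arm out may be nearer the truth.** The plan itself says "a family that drops out because the child is not losing weight will suggest non-ignorable missingness". If early FBT dropouts gain nothing, step 6 shows the existing list doing better than by-arm imputation. This stands as a reason to state the assumption openly; the plan does not present the omission as a choice.

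Three stronger readings are not supported. A reader might take 11–13% or more as the expected loss, but the half-baseline-only split and the absence of recovery have no source in the documents. An effect growing linearly to 24 months would lose more, but the plan expects faster early change. A reader might also infer from "the effect size gets smaller as length of follow-up increases, up to approximately the five-year follow-up" that the effect wanes before month 24, which would offset the loss. That sentence describes follow-up after treatment ended in a 10-year dataset, whereas FBT here runs to month 24. I quote no power loss: a simplified simulation of the design did not reproduce the plan's Table 1, so its absolute power levels are unreliable.

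**Conclusion.** The concern holds and should be fixed. As written, item 3 gives a primary estimate biased toward zero whenever the true effect is non-zero and data are missing at random given arm. The omission is certain from the text; whether the analysis code would repeat it is not. The practical size cannot be settled from the documents, because it depends on the baseline-only share remaining after item 2. It is minor if follow-up matches the earlier trial and material only if early loss is much heavier and chart recovery limited. The percentages for children with interim visits rest on the assumed levelling-off shape and correlation structures; the zero contrast for baseline-only children does not.

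The parent analysis inherits the same flaw. Its recovery route is less certain, since item 2 names only pediatrician visits, although the withdrawal section allows data from participants' physicians.

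**What to change.** Amend B.7 item 3 to say that multiple imputation is run separately within each randomised arm, or that the imputation model includes arm and its interactions with the earlier measurements. Use the same wording for sensitivity analysis 1 and for the parent analysis (Secondary Aim 1).

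Because by-arm imputation assumes that dropouts share the effect seen in their arm, add one sensitivity analysis that imputes FBT children with no follow-up from the UC distribution (control-based imputation). Reporting by arm how many children fall under items 1, 2 and 3, and how many of the last group have baseline data only, would let readers judge the size directly.

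The cost is one sentence of SAP wording, a by-arm statement in PROC MI and one extra run, with no new data. The downside is the assumption now made explicit: if early FBT dropouts gain no benefit, by-arm imputation overstates the intention-to-treat effect, and the control-based run is there to show by how much.

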The DCC will organize annual site visits to all clinics that will focus on a detailed review of study procedures. Special additional site visits may occur if routine quality control measures determine that a clinic is having difficulty with some aspect of the protocol. Site visitors will prepare an agenda that will include observations of the performance of study procedures and of the filing system that is used to store completed data forms. They will confirm that data forms are correctly filed, that IRB approvals are available, and that changes on forms are appropriately initialed and dated by the person who made the changes. In addition, site visitors may do random data audits in accordance with section **X.F.2**. Site visits will generally be conducted by a DCC staff person and by an investigator from another clinic.

III. Statistical Considerations

A. Statistical Analysis Plan

Data will be analyzed with SAS using the intention-to-treat principle. P-values less than 0.05 will be considered significant and all tests are two-sided. Details of how the intention-to-treat principle will be implemented are contained in a later section.

B. Primary Analysis

The primary goal of this study is to determine whether the change in weight status among children who have overweight/obesity (*Primary Specific Aim 1, DSMB approved protocol addenda, 11.2.18*) is superior among those who are randomized to family-based treatment (FBT) as compared to those who are randomized to usual care (UC) when treated in a primary care setting. The primary outcome measure in children is the percent over the age- and sex-specific 50th BMI percentile. The specific question of interest in the primary analysis is whether the change from baseline to 24 months in the intervention group is greater in the FBT group than in the UC group.

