Power computations for PLAN employ simulations and two-sided tests at the 0.05 level of significance. The simulations reflect the planned primary analysis of covariance and the fact that this is an individually randomized group treatment trial with the coach (N=3 per site) nested within the site (N=4 sites) in the FBT group but with no such nesting in the UC group. The analysis of covariance that is simulated in the power computations treats the 24-month value of the outcome measure as the dependent variable and the baseline value as a covariate. The use of this approach reflects the primary study goal of comparing 24-month values across groups, with the outcome being compared being percent over normalized BMI in the participating child. Each result is based on 1000 simulations.

Tabulated power values employ sample sizes of 528 and that are between 65% and 95% of that total. Effect size estimates are generated using considerations and preliminary data discussed below. Usual care data involving an intervention and subjects most similar to our UC group is provided by Kalarchian⁶¹ who randomized 81 8-12-year-old children with obesity to a usual care control condition and found an average percent overweight change of -0.17 ± 10.08 at 1 year. We expect some deterioration in this group at 2 years but will assume conservatively for the purpose of power computations that the two-year change will be 0 ± 10.08 in the UC group in the proposed research. Our estimated change in the FBT group begins with a review of seven studies^{20,62-67} authored by [name]. There were 314 overweight/obese children in those studies who received FBT interventions similar to the one we will employ. When we combined

the data for those 314 children, we found an overall average decrease in percent over BMI of 10.6 ± 15.3 at 24 months.

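### Imputation of the missing 24-month primary outcome lists raw height and weight, states no scale or model form, and leaves out treatment group: a modest loss of precision from the scale, and an effect pulled towards zero from the missing group term.

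*Combined protocol and SAP*

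**What the plan says.** All references are to the Statistical Considerations chapter of the combined protocol and SAP unless stated otherwise.

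- **Outcome and model (B, Primary Analysis).** "The primary outcome measure in children is the percent over the age- and sex-specific 50th BMI percentile". The primary model is an analysis of covariance "with the 24-month value as the dependent variable and with the baseline value as a predictor variable". It also contains the intervention term and a coach-level random effect in the FBT arm.
- **When a value counts as missing (B.7, item 2).** The rule starts "If the 24-month value of height and/or weight (the defining components of the primary outcome) is missing". Item 2 first uses pediatric clinic measurements within 30 days of the target date. Failing that, it interpolates between clinic measurements within three months on each side.
- **Last resort (B.7, item 3).** If neither is available, "the 24-month value will be imputed using multiple imputation". On the model: "Variables that will be used to facilitate the imputation process will be baseline height and weight, age, sex, and race". On later visits: "Any height and weight data collected using PLAN assessments at 6, 12, or 18 months will also be included in the multiple imputation".

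Item 3 does not say whether the imputed quantity is height and weight or percent over BMI, and it gives no functional form or transformation. Percent over BMI is named as a predictor at no visit. Treatment group and coach are not listed.

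**The concern.** Percent over BMI is a ratio: weight divided by height squared, divided by the median BMI for age and sex. A kilogram is worth more points in a small child than in a large one; on the growth curve assumed below, it is worth about twice as many points at age 6 as at age 12. A linear model in raw height and weight with one residual variance cannot respect that. It adds too much noise in young children and too little in older ones. If percent over BMI is imputed directly from the same raw variables, the model recovers the analysis covariate only through a poor linear approximation and leaves too much residual variance.

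The imputed values go straight into the primary analysis, so the excess noise widens the primary standard error. The same list also lacks the treatment group. Imputed children with no follow-up data would then show no group difference, and the estimated effect would move towards zero.

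**Working it through.** **1. Inputs from the documents.** There are 528 families, allocated 50/50, so 264 per arm. FBT has 12 coaches, hence 264/12 = 22 families each. The smallest difference is 5.3 points, with SD 12.7 or 15.3. The ICC is 0.01 in UC and 0.04 or more in FBT (B.1 and power Table 1). Planned dropout is 20% (Study Halting Rules for Participant Safety). The low case is 7 of 172 = 4.1%, from the earlier multicenter trial cited in B.6.

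**2. The plan's own power.** "Power computations for PLAN employ simulations and two-sided tests at the 0.05 level of significance". As a closed-form check:

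Var = SD²/264 × (1 + 21 × ICC_FBT) + SD²/264 × (1 + 21 × 0.01)

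With SD 12.7 and FBT ICC 0.04: 0.611 × 1.84 + 0.611 × 1.21 = 1.863, so SE = 1.365. A noncentral t with 11 df gives power 0.941, against 0.95 in Table 1. With SD 15.3 it gives 0.834, against 0.84. Rows tested up to ICC 0.10 agree within 2 points; the ICC 0.15 rows come out about 3 points high.

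**3. Simulation.** 528 children, effect -5.3, SD 12.7, 20 imputations by normal linear regression, Rubin's rules, ANCOVA on baseline, 300 to 500 replicates per scenario.

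Assumptions not in the documents:
- a median BMI curve starting near 15.3 at age 6;
- about 11.5 cm of growth in two years;
- baseline percent over BMI with SD about 15 to 32;
- values missing completely at random;
- no coach variance.

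In the table, reading (a) imputes height and weight and reading (b) imputes percent over BMI from the raw variables. The comparator imputes percent over BMI from its own earlier values. Treatment group is left out of all three, as in the plan's list.

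| Scenario | SE (a) | SE (b) | SE comparator | Excess (a) | Excess (b) |
|---|---|---|---|---|---|
| 20% missing, baseline data only | 1.294 | 1.342 (1.283 to 1.392 over the baseline SD range) | 1.230 | 5% | 9% (4% to 13%) |
| 20% missing, all interim visits | 1.153 | 1.262 | 1.135 | 1.6% | 11% |
| 4.1% missing, baseline data only | 1.145 | 1.157 | 1.131 | 1.2% | 2.3% |

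Separate runs with treatment group in the model and baseline data only gave the following:
- At 20% missing: 1.324 (a) and 1.371 (b) against 1.252, or 6% and 10%.
- At 4% missing: 1.144 and 1.153 against 1.131, or 1% and 2%.
- Under (a) with 18-month data available, the excess was 0.5% to 1%.

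**4. Spread by age.** The SD of imputed change at 20% missing with baseline data only, where the true value is about 12.9 at every age:
- (a): 18.4 in the youngest third and 10.5 in the oldest, a ratio of 1.75. With interim visits: 14.3 and 12.3.
- (a) with baseline percent over BMI added as a predictor: 18.4 and 10.6, SE 1.292. Nothing changes, so the cause is the scale and not the missing covariate.
- (b): 17.7 and 16.7, too wide but nearly equal by age. Adding baseline percent over BMI restores 12.8 and 12.8, with SE 1.229.

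**5. Effect estimate.** At 20% missing with baseline data only and no group term, (a), (b) and the comparator gave -4.30, -4.30 and -4.29, so the scale does not move the estimate. The group term does. With group included, (a) gave -5.43 and the comparator -5.36; full data gave -5.34. The expected attenuation is (1 - 0.20) × 5.3 = 4.24, which matches. With all interim visits the estimate without group was -5.22, against -5.21 for full data, but the simulation assumed the full effect was present by 18 months.

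**6. Size on the power scale.** Starting from 0.941, a 1.5% larger SE gives 0.935, 5% gives 0.919 and 9% gives 0.899. A 20% smaller effect gives 0.807.

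**The case against.** The strongest reply is that item 3 fixes no model, so the defect lies in a model supplied by the reader. PROC MI is named in B.6 for the random coefficient models, where imputation is a sensitivity analysis, and not for item 3. B.8 promises attention to assumptions and mentions transformations. That stands: the text is under-specified and does not commit to a wrong model. But B.8 illustrates its checks with t-tests and random coefficient models, and the variables that item 3 does list are raw height and weight.

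Second, the largest figures need 20% of children to reach item 3 with baseline data only. Clinic data and interpolation come first, and the section on risks to human subjects plans medical-record retrieval. In the earlier trial 5 of the 7 children missing at 24 months had 18-month data, leaving 2/172, about 1%, with neither. If 5/7 of missing children have 18-month data, the excess under reading (a) is about 2.7% at 20% missing, 1.5% at 10% and 0.7% at 4.1%. Coach variance at ICC 0.04 lowers these to about 2.0%, 1.1% and 0.5%. This also stands, although B.6 expects more dropout here than in that trial.

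Third, section E plans a modified intention-to-treat analysis, a complete-case repeat and random coefficient models. These would show a problem but do not repair the primary analysis.

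A reader might also infer that omitting baseline percent over BMI is what distorts the spread by age. It is not. That variable is computed from baseline height, weight, age and sex, all of which are listed, and adding it under reading (a) changed nothing. The age distortion and the covariate problem belong to different readings.

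**Conclusion.** The point holds in a limited form. Item 3 leaves the scale and form of the imputation open, and under either untransformed linear reading the listed variables do worse than a simple alternative.

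- **Scale.** The standard error is about 1% larger (a) or 2% larger (b) at 4% missing. At 20% missing with baseline data only it is 5-6% (a) or 4-13% (b) larger. Under (a) this falls to about 0.5-2% when 18-month or all interim data exist; under (b) interim visits did not help. The harm is lost precision.
- **Treatment group.** If the list is followed literally, the effect shrinks by roughly the fraction imputed among children with no interim data, about 20% at 20% missing. This is the larger of the two gaps.

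All sizes depend on the assumed growth curve, on data missing completely at random and on leaving out coach variance.

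Two stronger inferences are not supported. The scale problem does not bias the treatment effect: the estimates agreed across scales. Nor does it make Table 1 wrong: B.1 counts imputed values as data for all children, so the tabulated power does not depend on the imputation model. The halting-rules section says instead that dropouts were assumed to provide no data; those two statements should be reconciled.

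**What to change.** Rewrite item 3 of B.7 to state the following:

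1. The imputed quantity is 24-month percent over BMI itself.
2. The predictors are percent over BMI at baseline and at 6, 12 and 18 months where available, with age, sex and race.
3. Treatment group is included, or imputation is done separately by arm, with coach accounted for in the FBT arm.
4. If only one of height or weight is missing at 24 months, the measured one is kept, the other is imputed on the log scale, and percent over BMI is then computed.

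The cost is a short SAP amendment and a few lines of code on data already collected. The coach term, with 12 coaches of about 22 families each, needs the most care. No material downside is apparent. The change should be fixed before outcome data are seen by group.
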